#### **9.4.1.4. Analyses on Exploratory Effectiveness Endpoints**

The other exploratory effectiveness variables will be descriptively summarized by ITN application groups. The continuous variables will be summarized with count, mean, standard deviation, median, minimum, and maximum. The categorical variables will be presented with the count and percentage in each category.

The details of the statistical analyses and summary methods on each exploratory endpoint will be provided in the SAP.

### **9.4.2. Safety Analyses**

The safety analysis will be performed using the safety population. The numbers and percentage of participants reporting AEs will be tabulated regardless of causality. Frequency of device and procedure related AEs, as well as AESIs will be summarized.

#### **9.4.2.1. Adverse Events**

An AE or ADE will be considered a TEAE/TEADE if:

- The AE or ADE began on or after the date of the first application of study intervention; or
- The AE or ADE was present before the date of the first dose of study intervention, but increased in severity or became serious on or after the date of the first application of study intervention

An AE or ADE that occurs more than 30 days after the last dose of study intervention will not be counted as a TEAE or TEADE.

A SAE or SADE will be considered a TESAE or TESADE if it is a TEAE that additionally meets any SAE criteria or if it is a TEADE and meets SADE criteria.

Throughout the course of the study, all AEs will be reported and monitored on an AE CRF, including event name, duration, seriousness, relatedness, severity, action taken, and outcome. If AEs occur, the first concern will be the safety of the study participants.

Protocol 1919-802-019

[REDACTED]  
Intranasal Tear Neurostimulator

All events and device deficiencies are to be recorded on the corresponding CRF for the participant upon the site becoming aware of said event.

TEAEs and TEADEs will be coded with the MedDRA. The number of participants with TEAEs and TEADEs will be summarized by study intervention group for SOC and PT. TEAEs and TEADEs will also be summarized based on intensity and relationship to study intervention.

TESAEs and TESADEs will also be summarized by study intervention group for SOC and PT.

A listing of AEs, ADEs, and pregnancy test results will be also presented.

The definitions of AE/ADE and SAE/SADE can be found in [Appendix 2](#).

Intranasal Tear Neurostimulator

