## 4. Study Design

### 4.1. Overall Design

This is a prospective, randomized, controlled, parallel-group, open-label, single-center study in participants with DED.

This study consists of 2 visits: Screening and the Application Visit (Day 0). A study schema is located in Section 1.2 and the Schedule of Visits and Procedures is located in Section 1.3.

Participants will be randomized (in a 2:1 ratio) at Screening to either intranasal or extranasal acute (single) application of the ITN, which they will apply accordingly for approximately 3 minutes during the Application Visit. Approximately 36 participants with DED will be enrolled at a single site in the United States.

At Screening, and prior to any testing, participants will be provided with an IRB-approved ICF which they will have the opportunity to review and ask questions about before written consent is obtained. The Screening Visit should occur 30 to 60 days prior to the Application Visit.

The Application Visit will be separated into pre-ITN application and post-ITN application assessments. CDVA, slit-lamp examination, TMH measurement via OCT, and tear collection will occur at least 45-minutes prior to ITN application, and will be performed again following ITN application. Impression cytology will be performed following these procedures after ITN application.

Safety measures will be assessed before and after ITN application at the Application Visit, including CDVA and slit-lamp biomicroscopy. AEs will be queried prior to study exit.

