### 6.1. Study Interventions Administered

Study Intervention	TrueTear Intranasal Tear Neurostimulator (ITN) – Intranasal Application	TrueTear Intranasal Tear Neurostimulator (ITN) – Extranasal Application (Control)
Number and Timing of Interventions	Single application at Application Visit	Single application at Application Visit
Manufacturer	Allergan	Allergan

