## 8.4. Safety Assessments

### 8.4.1. Corrected Distance Visual Acuity

[figure not shown]
CDVA is performed at the Screening Visit and Application Visit. At the Application Visit, it is performed both prior to and after ITN stimulation. Any changes from baseline should be evaluated for possible reporting as an AE.

A large black rectangular box redacting the majority of the page content.

Protocol 1919-802-019

Intranasal Tear Neurostimulator

Protocol 1919-802-019

Intranasal Tear Neurostimulator

Approval Date: 04-Mar-2019

[figure not shown]
Protocol 1919-802-019

Intranasal Tear Neurostimulator

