## Intranasal Tear Neurostimulator

### **8.6.1. Time Period and Frequency for Collecting Adverse Event/Adverse Device Effect and Serious Adverse Event/Serious Adverse Device Effect Information**

All SAEs/SADEs from the signing of the ICF will be collected at the timepoints specified in the Schedule of Visits and Procedures (Section 1.3), and as observed or reported spontaneously by study participants.

All AEs/ADEs from the signing of the ICF will be collected at the timepoints specified in the Schedule of Visits and Procedures (Section 1.3), and as observed or reported spontaneously by study participants.

Medical occurrences that begin before the start of study intervention, but after obtaining informed consent, will be recorded in the AE section of the CRF.

All SAEs/SADEs will be recorded and reported to the sponsor or designee within 24 hours, as indicated in [Appendix 2](#). The investigator will submit any updated SAE/SADE data to the sponsor within 24 hours of it being available.

The investigator is not obligated to actively seek AE/ADE or SAE/SADE information after conclusion of study participation. However, if the investigator learns of any SAE/SADE, including a death, at any time after a participant has been discharged from the study, and he/she considers the event to be reasonably related to the study intervention or study participation, the investigator must promptly notify the sponsor.

The method of recording, evaluating, and assessing causality of AEs/ADEs and SAE/SADEs and the procedures for completing and transmitting SAE/SADE reports are provided in [Appendix 2](#).

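### The treatment-emergent rule uses the calendar date of the single application, so an adverse event that starts or worsens before stimulation on Day 0 is counted as treatment-emergent

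*Protocol*

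**What the plan says.** - **Start of the window.** Protocol Section 9.4.2.1 has two limbs. The first takes any event for which "The AE or ADE began on or after the date of the first application of study intervention". The second takes an event present before that date that became more severe, or became serious, on or after it. Both limbs work by date and neither mentions a clock time.
- **End of the window.** The same section says that an event that "occurs more than 30 days after the last dose of study intervention will not be counted as a TEAE or TEADE".
- **Exposure.** Section 6.1 gives both groups the same schedule: "Single application at Application Visit". First and last application are therefore one event, on Day 0.
- **Order of the visit.** Section 4.1 divides the Application Visit into assessments before and after application: "CDVA, slit-lamp examination, TMH measurement via OCT, and tear collection will occur at least 45-minutes prior to ITN application". These are repeated after application, and impression cytology follows.
- **What is recorded.** Section 8.6.1 collects adverse events from consent, including those that begin before the intervention. Section 8.4.1 adds, for visual acuity, "Any changes from baseline should be evaluated for possible reporting as an AE".
- **End of collection.** Section 1.1 makes Day 0 the exit day, and Section 4.1 puts the adverse event query before exit. Section 8.6.1 then says "The investigator is not obligated to actively seek AE/ADE or SAE/SADE information after conclusion of study participation". The exception is a serious event that the investigator learns of and considers reasonably related.

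**The concern.** A treatment-emergent rule should separate events that could follow the intervention from those that could not. A date serves that purpose when treatment runs over many days. Here one stimulation of about 3 minutes takes place partway through a visit that is built as a before-and-after comparison, and a date cannot order events within that visit. Irritation caused by the pre-application tear collection, for example, would enter the TEAE tables by study intervention group alongside events that did follow stimulation. In groups of 24 and 12, a single event of this kind is visible in a percentage.

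The upper limit raises a smaller point. It allows counting to 30 days, but scheduled collection stops on Day 0. A reader of the tables could take the counts for a 30-day incidence unless told otherwise.

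**Working it through.** The protocol gives no figure on this point to reproduce. The check applies the rule to example events, once by date as written and once by the start of the application.

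**Step 1: onset.** Inputs are the date rule and 30-day cap (Section 9.4.2.1), one application on Day 0 (Sections 1.1 and 6.1), pre-application tests at least 45 minutes earlier (Section 4.1), and Screening 30 to 60 days earlier (Section 4.1).

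| Onset of a new event | Date rule | Start-of-application rule |
|---|---|---|
| Screening, Day -30 | not TEAE | not TEAE |
| Day 0, at tests 45 minutes before application | **TEAE** | **not TEAE** |
| Day 0, during application | TEAE | TEAE |
| Day 0, after application | TEAE | TEAE |
| Day 1 | TEAE | TEAE |
| Day 31 | not TEAE | not TEAE |

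Only one row changes: an event that starts on Day 0 before stimulation.

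**Step 2: worsening.** The second limb behaves the same way. An event that was present before Day 0 and worsens during the pre-application tests meets it as written, and would not meet it if worsening were timed from the start of the application.

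**Step 3: TEAE or TEADE.** Appendix 2 defines an ADE as an adverse event related to use of the device, and its causality scale lists an incompatible time relationship under the not-related category. The row that changes is therefore a TEAE under the date rule, but a TEADE only if causality is also attributed to the device.

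**Step 4: size per participant.** The planned group sizes are 24 and 12 (Section 9.2). One participant whose only TEAE arose before application moves incidence by:

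- intranasal: 1/24 = 4.2 percentage points
- extranasal: 1/12 = 8.3 percentage points

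These are sensitivities to one participant. The expected bias would be the number of such participants times these values, and the protocol gives nothing from which to estimate that number.

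**Step 5: upper limit.** The last scheduled query is on Day 0, so scheduled collection of new events after exit covers 0 of the 30 days. Within that period the cap can act only on spontaneous reports.

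**The case against.** Several points on the other side are sound.

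- **Device effects.** A reader might infer that events before stimulation are counted as device effects. The documents do not support that. The TEADE class needs a judgement of device-relatedness, and Section 9.4.2.1 also summarizes TEAEs by relationship to the intervention.
- **Follow-up.** A reader might infer that the 30-day sentence promises follow-up that is not carried out. It does not. It is an exclusion from counting, it commits nobody to a contact, and it still governs spontaneous reports. Section 8.6.3 also has known events followed until they resolve or stabilize. No text labels the tables as 30-day incidence.
- **The rule as a whole.** The date rule correctly excludes events that start and stay unchanged within the 30 to 60 days from Screening, including those from the Screening impression cytology. Only part of one visit is ambiguous.
- **First seen is not first begun.** An acuity or slit-lamp change found before application may have begun earlier, and Section 9.4.2.1 classifies by onset. Appendix 2 also says that, for devices, disease signs that predate the intervention are not adverse events. The baseline meant in Section 8.4.1 cannot be confirmed because the surrounding text is redacted. The clearest cases are new events caused by the pre-application tests.
- **Limit of the remedy.** Most of the same tests are repeated after stimulation and impression cytology follows. Events from those procedures remain TEAEs under either rule, so relatedness must still separate device from procedure.
- **What is not visible.** The Schedule of Activities and the Visit 2 detail are redacted and the CRF is not shown. Onset time may already be collected, and a SAP could refine the rule.

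These points limit the consequence but leave the classification error. The protocol states a rule by date, and followed literally it gives the wrong class to a pre-application Day 0 event even if the time is on record.

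**Conclusion.** The point holds as a minor error in a stated definition. Both limbs count as treatment-emergent an event that starts or worsens on Day 0 before the participant has been stimulated.

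The direction is toward over-counting. The protocol describes the same pre-application tests for both groups, so the error should be similar in each and is unlikely to favor one. Its size is unknown. The 4.2 and 8.3 points bound what one participant can do at the planned group sizes and do not forecast the bias. The conclusion assumes that the definition is applied as written and that no unseen document overrides it.

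On the upper limit, the finding is only that the cap and the scheduled collection period differ, and that the tables should say so. Sample size and the primary analysis are unaffected.

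**What to change.** 1. In Section 9.4.2.1, define onset as at or after the start of the ITN application, and define worsening (in severity or to serious) as at or after the same point. Change both limbs.
2. Classify every Day 0 adverse event as before or after application. If the CRF does not already collect an onset time or a before/after flag, add one.
3. Use the Day 0 pre-application acuity and slit-lamp findings as the reference for treatment-emergent worsening. Both are already scheduled.
4. Keep the 30-day limit as a counting cap, so that a later spontaneous report stays in the TEAE tables. Add a table note that scheduled adverse event collection ends at study exit on Day 0 and that later events are spontaneous reports only.

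The cost is a revised definition, a table footnote and at most one data item. No visit, procedure or participant is added.

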## **10. Supporting Documentation and Operational Considerations**

### **10.1. Appendix 1: Regulatory, Ethical, and Study Oversight Considerations**

#### **10.1.1. Regulatory and Ethical Considerations**

- This study will be conducted in accordance with the protocol and with the following:
  - Consensus ethical principles derived from international guidelines including the Declaration of Helsinki and Council for International Organizations of Medical Sciences International Ethical Guidelines
  - Applicable ICH/ISO GCP guidelines
  - Applicable laws and regulations
- The protocol, protocol amendments, ICF, IB, and other relevant documents (eg, advertisements) must be submitted to an IRB/IEC by the investigator and reviewed and approved by the IRB/IEC before the study is initiated.
- Any amendments to the protocol will require IRB/IEC approval before implementation of changes made to the study design, except for changes necessary to eliminate an immediate hazard to study participants.
- The investigator will be responsible for the following:
  - Providing written summaries of the status of the study to the IRB/IEC annually or more frequently in accordance with the requirements, policies, and procedures established by the IRB/IEC
  - Notifying the IRB/IEC of SAEs or other significant safety findings as required by IRB/IEC procedures
  - Providing oversight of the overall conduct of the study at the site and adherence to requirements of applicable local regulations, for example 21 CFR, ICH guidelines, the IRB/IEC, and European regulation 536/2014 for clinical studies (if applicable)

#### **10.1.2. Financial Disclosure**

Investigators and subinvestigators will provide the sponsor with sufficient, accurate financial information as requested to allow the sponsor to submit complete and accurate financial certification or disclosure statements to the appropriate regulatory authorities. Investigators are responsible for providing information on financial interests during the course of the study and for 1 year after completion of the study.

Intranasal Tear Neurostimulator

#### **10.1.3. Informed Consent Process**

- The investigator or his/her representative will explain the nature of the study to the participant or his/her legally authorized representative and answer all questions regarding the study.
- Participants must be informed that their participation is voluntary. Participants will be required to sign a statement of informed consent that meets the requirements of 21 CFR 50, local regulations, ICH guidelines, HIPAA requirements, where applicable, and the IRB/IEC or study center.
- The medical record must include a statement that written informed consent was obtained before the participant was enrolled in the study and the date the written consent was obtained. The authorized person obtaining the informed consent must also sign the ICF.
- Participants must be re-consented to the most current version of the ICF(s) during their participation in the study.
- A copy of the ICF(s) must be provided to the participant or the participant's legally authorized representative.

#### **10.1.4. Data Protection**

- Participants will be assigned a unique identifier. Any participant records or datasets that are transferred to the sponsor will contain the identifier only; participant names or any information which would make the participant identifiable will not be transferred.
- The participant must be informed that his/her personal study-related data will be used by the sponsor in accordance with local data protection laws. The level of disclosure must also be explained to the participant.
- The participant must be informed that his/her medical records may be examined by Clinical Quality Assurance auditors or other authorized personnel appointed by the sponsor, by appropriate IRB/IEC members, and by inspectors from regulatory authorities.

#### **10.1.5. Posting Clinical Study Data**

- Study data and information may be published in nonpromotional, peer-reviewed publications either by or on behalf of the sponsor.
- Clinical study reports, safety updates, and annual reports will be provided to regulatory authorities as required.
- Company-sponsored study information and tabular study results will be posted on the United States National Institutes of Health's website [www.ClinicalTrials.gov](http://www.ClinicalTrials.gov) and other publicly accessible sites

Intranasal Tear Neurostimulator

#### **10.1.6. Data Quality Assurance**

- All participant data relating to the study will be recorded on printed CRFs unless transmitted to the sponsor or designee electronically (eg, laboratory data). The investigator is responsible for verifying that data entries are accurate and correct by signing the CRF.
- The investigator must maintain accurate documentation (source data).
- The investigator must permit study-related monitoring, audits, IRB/IEC review, and regulatory agency inspections and provide direct access to source data documents.
- The sponsor or designee is responsible for the data management of this study including quality checking of the data.
- Study monitors will perform ongoing source data verification to confirm that data entered into the CRF by authorized site personnel are accurate, complete, and verifiable from source documents; that the safety and rights of participants are being protected; and that the study is being conducted in accordance with the currently approved protocol and any other study agreements, ICH GCP, and all applicable regulatory requirements.
- Records and documents, including signed ICFs, pertaining to the conduct of this study must be retained by the investigator as stated in the clinical trial agreement. No records may be destroyed during the retention period without the written approval of the sponsor. No records may be transferred to another location or party without written notification to the sponsor.

#### **10.1.7. Source Documents**

- Source documents provide evidence for the existence of the participant and substantiate the integrity of the data collected. Source documents are filed at the investigator's site.
- Data reported on the CRF that are transcribed from source documents must be consistent with the source documents or the discrepancies must be explained. The investigator may need to request previous medical records or transfer records, depending on the study.
- Definition of what constitutes source data can be found in Section 4.0 of ICH E6, GCP: Consolidated Guidance and records must be attributable, legible, contemporaneous, original, and accurate.

#### **10.1.8. Study and Site Closure**

The sponsor designee reserves the right to close the study site or terminate the study at any time for any reason at the sole discretion of the sponsor. The study site will be closed upon study completion. A study site is considered closed when all required documents and study supplies have been collected and a study-site closure visit has been performed.

The investigator may initiate study-site closure at any time, provided there is reasonable cause and sufficient notice is given in advance of the intended termination.

Reasons for the early closure of a study site by the sponsor or investigator may include but are not limited to:

## Intranasal Tear Neurostimulator

- Failure of the investigator to comply with the protocol, the requirements of the IRB/IEC or local health authorities, the sponsor's procedures, or GCP guidelines
- Inadequate recruitment of participants by the investigator
- Discontinuation of further study intervention development

### **10.1.9. Publication Policy**

- Allergan as the sponsor has proprietary interest in this study. Authorship and manuscript composition will reflect joint cooperation between investigators and Allergan personnel. Authorship will be established prior to the writing of the manuscript.
- The sponsor will comply with the requirements for publication of study results.
- Authorship will be determined by mutual agreement and in line with International Committee of Medical Journal Editors authorship requirements.

### **10.1.10. Compliance with Protocol**

The investigator is responsible for compliance with the protocol at the investigational site. A representative of the sponsor will make frequent contact with the investigator and his/her research staff and will conduct regular monitoring visits at the site to review participant and study intervention accountability records for compliance with the protocol. Protocol deviations will be discussed with the investigator upon identification. The use of the data collected for the participant will be discussed to determine if the data are to be included in the analysis. The investigator will enter data that may be excluded from analysis as defined by the protocol deviation specifications. Significant protocol deviations will be reported to the IRB/IEC according to the IRB/IEC's reporting requirements.

Intranasal Tear Neurostimulator

